11.10. Statistical Analysis Process

The clinical study will be analyzed by the Sponsor.

The SAP will provide the statistical methods and definitions for the analysis of the efficacy and safety data, as well as describe the approaches to be taken for summarizing other clinical study information such as subject disposition, demographic and baseline characteristics, study drug exposure, and prior and concomitant medications. The SAP will also include a description of how missing, unused, and spurious data will be addressed.

To preserve the integrity of the statistical analysis and clinical study conclusions, the SAP will be finalized prior to database lock.

All statistical analyses will be performed using SAS® Version 9.2 or higher (SAS Institute, Cary, North Carolina 27513).

11.11. Specification of Modified Continuous Reassessment Method with Escalation With Overdose Control

In this study mCRM will be based on a 2-parameter BLRM, as defined below.

11.11.1. Bayesian Logistic Regression Model for Modified Continuous Reassessment Method

The dose-toxicity relationship for mCRM with EWOC principle will be described by a 2-parameter BLRM:

$$\text{logit}(\pi(d)) = \log(\alpha) + \beta \log(d/d^*), \quad \alpha > 0, \beta > 0$$

where $\text{logit}(\pi(d)) = \ln(\pi(d)/(1-\pi(d)))$, and $\pi(d)$ is the probability of a DLT or DLT rate at dose d . Doses are rescaled as d/d^* with the reference dose $d^* = 800$ mg. As a consequence, α is equal to the odds of toxicity at d^* . Note that for a dose equal to zero, the probability of toxicity is zero.

11.11.2. Prior Specification for Bayesian Logistic Regression Model Parameters

The Bayesian approach requires the specification of a prior distribution for the BLRM parameters. A minimally-informative bivariate normal prior for the model parameters $(\log(\alpha), \log(\beta))$ is obtained as follows:

- The best guess of the MTD is projected to be around 800 mg in humans. The median prior probabilities of DLT are set to be approximately 8% and 24.5% at 200 mg (projected starting dose for dose escalation using mCRM) and the projected MTD of 800 mg, respectively.
- For the remaining doses, the prior medians of probability of DLT are assumed linear in log-dose on the logit-scale.
- Based on the above medians for the probability of DLT at each dose and wide prior credible intervals (obtained from minimally informative Beta distributions), the optimal parameters of the bivariate normal distribution can be obtained as follows:

Parameters	Means	Standard Deviations	Correlation
$\log(\alpha), \log(\beta)$	(-1.1493, -0.5514)	(2.0739, 1.5228)	-0.1943

11.11.3. Escalation With Overdose Control Principle

Dose recommendation for the next cohort of patients will be based on summaries of the posterior probability of DLT rate for provisional doses.⁴⁴ After each cohort of subjects completes DLT evaluation during Cycle 1, the joint posterior distribution of the BLRM parameters will be generated according to the Bayes' theorem based on the likelihood function of the accumulated DLT data from Cycle 1 and the prior distribution. Posterior probabilities of DLT rate at different dose levels will then be obtained from updated BLRM, and summarized for DLT rate in 4 different ranges: under-dosing (ie, DLT rate within [0, 0.16]), target toxicity (ie, DLT rate within [0.16, 0.33]), excessive toxicity (ie, DLT rate within [0.33, 0.60]), and unacceptable toxicity (ie, DLT rate within [0.60, 1.00]). The dose level recommended by mCRM for dosing next cohort will be based on these probabilities according to the EWOC principle. The EWOC principle requires that the mCRM recommended dose for the next cohort of subjects is the one with the highest posterior probability of the DLT rate in the target DLT rate range of [0.16, 0.33] among all doses fulfilling the overdose control constraint that there is less than 0.25 of probability for DLT rate > 0.33 (probability for excessive or unacceptable toxicity).

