3.2.1.2. Cycle 1 and Beyond (Combination Therapy)

In Cycle 1 and beyond, DS-1205c will be taken BID in combination with 250 mg QD of gefitinib in 21-day cycles, as outlined in detail in the Schedule of Events, Dose Escalation, (Cycle 1 and Beyond) ([Table 6.2](#)).

Dose escalation of DS-1205c to determine the RDE will be guided by the modified Continuous Reassessment Method (mCRM) using a Bayesian logistic regression model (BLRM) following the escalation with overdose control (EWOC) principle (Section [11.11](#)). The logistic regression model for the dose-response (DLT rate) relationships will include 2 parameters: the intercept and slope. The DLT-evaluation period is defined as the 7 days of Cycle 0 plus the 21 days of Cycle 1 (28 days total). A DLT-evaluable subject is defined as a subject who has received DS-1205c and either has completed minimum safety evaluation requirements over the DLT-evaluation period or has experienced a DLT during the DLT-evaluation period. After at least 3 DLT-evaluable subjects of each cohort complete DLT evaluation, posterior distributions of DLT rate will be derived for all dose levels based on the BLM using DLT outcome data from all assessed doses and a pre-specified prior distribution for the model parameters. The EWOC principle requires that the mCRM-recommended dose for the next cohort of subjects is the one with the highest posterior probability of the DLT rate in the target DLT rate interval with the overdose control constraint for excessive or unacceptable toxicity.

As an exception, the model will be reevaluated before enrollment of any additional subjects to the cohort if 2 DLT-evaluable subjects in the cohort experience DLT before the enrollment of the third subject. Enrollment of subjects to a new higher-dose cohort requires completion of DLT evaluation of at least 3 subjects treated in the current cohort. Subjects who have neither completed DLT evaluation nor experienced DLT will not be included in a BLM update. In the event when subjects in the previous cohort experience DLTs after enrollment of subjects to a new cohort has begun, dose level assignment of the next subject in the new cohort will be based on an updated BLM using DLT outcome data from all assessed doses. Subjects already receiving treatment will continue treatment at their assigned dose level or per dosing modification guidelines outlined in Section [5.4](#).

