Subjects can be backfilled (added) to lower doses previously proven to be safe at any point during Dose Escalation. Lower or intermediate dose levels may also be considered based on review of available safety, tolerability, and PK data in this and other studies with the investigational agent. There will be no intrasubject dose escalation.

Any dose cohort may be expanded to include additional subjects for further evaluation of safety or PK parameters as required. The dose level for next cohort will be chosen by the Sponsor as outlined in Section [11.11.3](#) based on the dose recommendation by the mCRM, clinical assessment of TEAEs, toxicity profiles, efficacy, PK, and PD information observed thus far.

The number of treatment cycles is not fixed. Subjects may continue study treatment until PD, unacceptable toxicity, withdrawal of consent, or other reasons detailed in Section 5.6.1.

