3.2.1.3. Dose-Limiting Toxicities (DLT)

A DLT is defined as any TEAE not attributable to disease or disease-related processes or to concomitant medications or procedures that occurs during the DLT-evaluation period (Cycle 0, Day 1 to Cycle 1, Day 21 of Dose Escalation) and is Grade 3 or above, according to NCI-CTCAE version 5.0, with the exceptions as defined below.

For hematological toxicities, a DLT is defined as follows:

Hematologic Dose-Limiting Toxicities (DLT) NCI-CTCAE version 5.0		
Hematological toxicity	NCI-CTCAE Grade	CTCAE version 5.0 Definition
Neutrophil count decreased	4 (Lasting > 7 days or neutrophil count decreased that requires supportive therapy with myeloid growth factors)	< 500/mm ³ ; < 0.5 × 10 ⁹ /L
Febrile neutropenia	≥ 3	Grade 3: ANC < 1000/mm ³ with a single temperature of > 38.3°C or a sustained temperature of ≥ 38°C for more than one hour Grade 4: Life-threatening consequences; urgent intervention indicated
Anemia	4	Life-threatening consequences; urgent intervention indicated
Platelet count decreased	≥ 3 Lasting > 7 days or with clinically significant hemorrhage	Grade 3: < 50,000 – 25,000/mm ³ ; < 50.0 – 25.0 × 10 ⁹ /L Grade 4: < 25,000/mm ³ ; < 25.0 × 10 ⁹ /L
Lymphocyte count decreased	4 Lasting ≥ 14 days	< 200/mm ³ ; < 0.2 × 10 ⁹ /L
Any	5	Death

For hepatic organ toxicities, a DLT is defined as follows:

Hepatic Dose-Limiting Toxicities (DLT) NCI-CTCAE version 5.0		
Hepatic Organ Toxicity	NCI-CTCAE Grade	CTCAE version 5.0 Definition
Serum aspartate aminotransferase (AST) increase	4	> 20.0 × the upper limit normal (ULN) if baseline was normal; > 20.0 × baseline if baseline was abnormal
Serum alanine aminotransferase (ALT) increase	4	> 20.0 × ULN if baseline was normal; > 20.0 × baseline if baseline was abnormal
AST or ALT increased	3 Lasting >5 days	> 5.0 – 20.0 × ULN if baseline was normal; > 5.0 – 20.0 × baseline if baseline was abnormal
ALT or AST increased $\geq 3.0 \times$ ULN with simultaneous TBL increased $\geq 2.0 \times$ ULN	Not applicable	Not applicable
Any	5	Death

For pulmonary toxicities, a DLT is defined as any of the following:

Pulmonary Dose-Limiting Toxicities (DLT) NCI-CTCAE version 5.0		
Pulmonary Toxicity	NCI-CTCAE Grade	CTCAE version 5.0 Definition
Confirmed interstitial lung disease (ILD)	1	Asymptomatic; clinical or diagnostic observations only; intervention not indicated
	2	Symptomatic; medical intervention indicated; limiting instrumental activities of daily living (ADL)

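### Section 11.11.3 feeds the dose-escalation model only Cycle 1 DLTs, contradicting the 28-day DLT window that starts in Cycle 0

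*Combined protocol and SAP*

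**What the plan says.** The model specification in 11.11.3 says that the posterior is generated "After each cohort of subjects completes DLT evaluation during Cycle 1" and that it is "based on the likelihood function of the accumulated DLT data from Cycle 1 and the prior distribution". It does not mention Cycle 0.

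Elsewhere the window is longer:

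- Section 3.2.1.2, and the synopsis in the same words: "The DLT-evaluation period is defined as the 7 days of Cycle 0 plus the 21 days of Cycle 1 (28 days total").
- Section 3.2.1.3 defines a DLT as an event that "occurs during the DLT-evaluation period (Cycle 0, Day 1 to Cycle 1, Day 21 of Dose Escalation").
- Section 3.2.1.2 on model updates: "Subjects who have neither completed DLT evaluation nor experienced DLT will not be included in a BLM update". A subject with a Cycle 0 DLT is not barred by this rule.
- Section 3.2.1.2 also requires the model to be re-evaluated early "if 2 DLT-evaluable subjects in the cohort experience DLT before the enrollment of the third subject", with no restriction to Cycle 1.
- Section 11.2 places a subject with a DLT in either cycle in the DLT-Evaluable Set.

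On the next dose, 3.2.1.2 refers the Sponsor to 11.11.3, and the same sentence says that the choice is "based on the dose recommendation by the mCRM, clinical assessment of TEAEs, toxicity profiles, efficacy, PK, and PD information observed thus far".

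For subjects without a DLT there are three evaluability tests. Section 11.2 asks for at least 75% of the Cycle 1 doses. Section 3.2.1.3 removes subjects who missed more than 25% of doses over Cycles 0 and 1 together, but only when the reasons are unrelated to adverse events. Section 3.2.1.2 refers to minimum safety evaluations that it does not list.

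**The concern.** Cycle 0 is a separate, named monotherapy period, so a reference to Cycle 1 data does not naturally include it. Section 11.11.3 is where a programmer would look for the likelihood, and 3.2.1.2 itself points there for the dose decision. No section says which wording prevails.

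The overdose-control constraint is the formal safeguard in the escalation algorithm, and the plan has no data monitoring committee (11.8, 15.9). If Cycle 0 DLTs stay out of the likelihood, the constraint is tested on incomplete data. The early re-evaluation in 3.2.1.2 shows this most clearly: if two Cycle 0 DLTs trigger it, a literal 11.11.3 would run it with neither event in the data.

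**Working it through.** **Inputs.** Model (11.11.1): logit π(d) = log α + β log(d/800). Prior (11.11.2): (log α, log β) bivariate normal with means (−1.1493, −0.5514), SDs (2.0739, 1.5228) and correlation −0.1943. Rule (11.11.3): a dose is admissible if P(π > 0.33) < 0.25. Among admissible doses, the pick is the one with the highest probability of a rate in the target range 0.16 to 0.33. Doses are 200, 400, 600 and 800 mg; d is taken as the amount per administration, as 11.11.2 implies by naming 200 mg as the starting dose.

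**The plan's own figures.** At 800 mg the log-dose term is zero, so the prior median is 1/(1 + exp(1.1493)) = 24.1% (plan: about 24.5%). Numerical integration gives 8.0% at 200 mg (plan: about 8%). The dose counts in 3.2.1.3 also reproduce, over both cycles: 0.75 × 56 = 42 DS-1205c doses, and 0.75 × 21 = 15.75, rounded up to 16 gefitinib doses.

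**Posterior.** Posterior ∝ prior × ∏ π(d)^x (1 − π(d))^(n − x), integrated on a two-dimensional grid. Cohort outcomes are illustrative. Left out means that the subject with the Cycle 0 DLT is absent from the likelihood.

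| Data | P(π > 0.33) at 200 / 400 / 600 / 800 mg | Admissible |
|---|---|---|
| One Cycle 0 DLT in three at 200 mg, counted: 1/3 | 0.368 / 0.486 / 0.555 / 0.598 | none |
| Same, left out: 0/2 | 0.065 / 0.108 / 0.162 / 0.239 | all four |
| 0/3 at 200 mg, then two Cycle 0 DLTs at 400 mg, counted: 2/2 | 0.381 / 0.616 / 0.732 / 0.782 | none |
| Same, left out: only 0/3 at 200 mg remains | 0.037 / 0.073 / 0.126 / 0.206 | all four |
| 0/3 at 200 mg, then one Cycle 0 and one Cycle 1 DLT in three at 400 mg, counted: 2/3 | 0.275 / 0.492 / 0.633 / 0.699 | none |
| Same, left out: 1/2 | 0.123 / 0.242 / 0.370 / 0.456 | 200 and 400; picks 400 |

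The first reversal does not depend on how the omission is coded. If the subject is kept but scored DLT-free (0/3 at 200 mg), the probability at 200 mg is 0.037 and all four doses are still admissible.

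**Evaluability of DLT-free subjects.** Section 11.2 needs 0.75 × 42 = 31.5, so 32 Cycle 1 doses of DS-1205c. Section 3.2.1.3 needs 42 of 56 over both cycles.

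- Counted per drug: 14/14 in Cycle 0 plus 28/42 in Cycle 1 is 42/56 = 75.0% overall, not excluded by 3.2.1.3. It is 28/42 = 66.7% of Cycle 1, which fails 11.2. This requires at least 16 of 21 gefitinib doses taken.
- Both drugs pooled (63 doses in Cycle 1, 77 in all): 14/14 plus 44 to 47 of 63 is 58/77 = 75.3% to 61/77 = 79.2% overall, not excluded. It is 44/63 = 69.8% to 47/63 = 74.6% of Cycle 1, which fails.

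If one such subject's status also decided entry to the model, then after 0/3 at 200 mg the data at 400 mg would be 1/3 or 1/4. With 1/3, P(π > 0.33) at 600 mg is 0.292 and the pick is 400 mg. With 1/4 it is 0.232 and the pick is 600 mg, where the target probability is 0.347 against 0.319 at 400 mg.

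**The case against.** The strongest reply is that one loose phrase stands against a consistent document. Sections 3.2.1.2, 3.2.1.3 and 11.2 and the Cycle 0 visit instructions in 6.1.2 all count Cycle 0 DLTs, and 3.2.1.2 cites 11.11, so the two should be read together. The literal reading would also defeat the early re-evaluation rule. This stands as evidence of intent. It does not remove the conflict, because 11.11.3 specifies the likelihood and 3.2.1.2 refers the dose choice there.

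Several stronger readings are tempting and are not supported:

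- That both references to Cycle 1 in 11.11.3 are errors. The timing phrase is true under the 28-day window, which ends on Cycle 1 Day 21. Only the likelihood phrase conflicts.
- That the evaluability mismatch changes dose recommendations. Section 11.6 ties the DLT-Evaluable Set to the DLT table, while 3.2.1.2 governs model updates. No section says that the 75% test in 11.2 feeds the model.
- That the per-drug example holds on DS-1205c alone. Section 3.2.1.3 also counts gefitinib. If both drugs are missed over the same continuous days, 28 to 30 of 42 DS-1205c doses leave only 14 to 15 of 21 gefitinib doses, and only 31 of 42 can leave 16. The pooled example does not need this condition.

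There is also real mitigation. Investigators report DLTs to the Sponsor in real time and safety review meetings address escalation (3.2.1.4), and the Sponsor weighs clinical data beyond the model (3.2.1.2).

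**Conclusion.** The likelihood sentence in 11.11.3 is wrong as written: it contradicts the DLT-evaluation period, the DLT-Evaluable Set and the update rule. Followed literally, it can turn a result with no admissible dose into one with all four admissible. In the 200 mg example the overdose probability at that dose moves from 0.368 to 0.065, across the 0.25 limit.

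This rests on the plan's stated prior, doses per administration and illustrative small cohorts. A reader might infer that the plan deliberately excludes Cycle 0 DLTs or that the trial would settle on a wrong dose. Neither follows: most of the text points the other way, and people as well as the model decide the dose. The documents give no Cycle 0 DLT rate, so how often this would matter is unknown.

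The evaluability mismatch is real but secondary. It affects the DLT table directly, and the model only if the same set is used for both.

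**What to change.** In 11.11.3, replace the restriction to Cycle 1 data in the likelihood sentence with DLT data from the DLT-evaluation period (Cycle 0 Day 1 to Cycle 1 Day 21), and refer to the inclusion rule in 3.2.1.2. Aligning the timing phrase is optional.

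Reconcile 3.2.1.2, 3.2.1.3 and 11.2 into one evaluability definition for DLT-free subjects. It should state the dosing period, whether doses are counted per drug or pooled, and how doses missed because of adverse events are treated. Say that this one definition serves both the model and the DLT table.

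The cost is wording in these sections. No new data are needed, because the Cycle 0 visits already call for DLT determination.

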3.2.1. Dose Escalation

3.2.1.1. Cycle 0 (Monotherapy, 7 Days)

To minimize the possibility of developing tumor flare with discontinuation of EGFR TKI, subjects who fulfill eligibility criteria will be instructed to continue their current EGFR TKI (gefitinib, erlotinib, afatinib, dacomitinib, or osimertinib) during screening. The last dose of gefitinib, erlotinib, afatinib, dacomitinib, or osimertinib must be taken 1 day before breakfast in clinic on Cycle 0, Day 1, as depicted in [Figure 3.1](#) above. This schedule provides an 8-day window between the last dose of gefitinib, erlotinib, afatinib, dacomitinib, or osimertinib, and the first dose of gefitinib.

Once eligibility is confirmed, subjects will be assigned by the Sponsor to receive DS-1205c at a specific dose level ([Table 3.1](#)). This will be either the current escalation dose (as determined by an algorithm described in detail in Section [3.2.1.2](#) below) or a previously assigned lower dose (ie, cohort backfilling).

Table 3.1: Dose Escalation Provisional Cohorts and Provisional Dosages

Cohort ^a	Cycle 0 Monotherapy (7-day cycle)	Cycle 1 and Beyond Combination Therapy (21-day cycles)	
	DS-1205c Dosage ^b	DS-1205c Dosage ^b	Gefitinib Dosage ^c
1	200 mg BID	200 mg BID	250 mg QD
2	400 mg BID	400 mg BID	250 mg QD
3	600 mg BID	600 mg BID	250 mg QD
4	800 mg BID	800 mg BID	250 mg QD

BID = twice daily; mg = milligrams; QD = once daily

- a. The second subject in each cohort should start dosing at least 24 hours after the initial dosing of the first subject. The cohort numbers in this table do not denote actual order of dose transition on the trial.
- b. Administer with a meal, with 240 mL of water. On the morning of Endpoint ECG days, breakfast should be started 30 minutes prior to dosing and should be completed within approximately 20 minutes. For all other dosings, it is recommended that meals (breakfast or dinner) be completed within approximately 30 minutes; DS-1205c should be taken immediately after meal completion. Doses of DS-1205c should be taken approximately 12 hours apart.
- c. Co-administer with morning dose of DS-1205c.

Subjects will report to the clinic on Day 1 before Cycle 0 to obtain ECGs at specified time points outlined in the Schedule of Events, Dose Escalation (Cycle 0) (see [Table 6.1](#)). These time points will be time matched to ECGs obtained on Cycle 0, Day 1.

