3.2.1.4. Safety Review Meetings

Investigators will communicate with the Sponsor any incidence of DLT on a real-time basis.

Safety review meetings (SRMs) will include at least the Investigators and the Sponsor's medical monitor.

During Dose Escalation, SRMs will occur as needed to make determinations about enrollment and dose escalation according to the DLT-dependent mCRM, and to determine the RDE.

During Dose Expansion, SRMs will occur as needed to assess safety and tolerability of the selected RDE.

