3.2.1.5. Stopping Rule for Recommended Dose for Expansion Determination

Dose Escalation will be stopped if any of the following occur:

- a. at least 6 evaluable subjects have been enrolled at the RDE level with at least 18 evaluable subjects, in total, enrolled in Dose Escalation, OR
- b. at least 9 evaluable subjects have been enrolled at a particular dose level, the model recommends continuing at the same dose level, and the posterior probability of the DLT rate falling within the target DLT interval is $\geq 50\%$.
The target DLT interval is defined as $16\% < \text{DLT rate} \leq 33\%$
(Section 11.11.3), OR
- c. the initial dose level is too toxic.

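### With the printed prior, 0/3 DLTs at 200 mg BID leads the model to recommend 800 mg BID with no stated limit on the step; after 1/3 no listed dose meets the overdose limit, and the plan does not say what follows.

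*Combined protocol and SAP*

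**What the plan says.** The dose-toxicity model is a two-parameter Bayesian logistic regression with reference dose 800 mg (Section 11.11.1). Section 11.11.2 gives the prior and its anchor: "The best guess of the MTD is projected to be around 800 mg in humans". Under Section 11.11.3 the recommended dose is the one with the highest posterior probability of the target interval among all doses meeting the "overdose control constraint that there is less than 0.25 of probability for DLT rate > 0.33".

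Table 3.1 lists 200, 400, 600 and 800 mg BID. Its footnote a adds: "The cohort numbers in this table do not denote actual order of dose transition on the trial". The condition for going up is in Section 3.2.1.2: "Enrollment of subjects to a new higher-dose cohort requires completion of DLT evaluation of at least 3 subjects treated in the current cohort".

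The same section lets the sponsor choose the next dose "based on the dose recommendation by the mCRM, clinical assessment of TEAEs, toxicity profiles, efficacy, PK, and PD information observed thus far", allows lower or intermediate doses to be considered, and states: "Any dose cohort may be expanded to include additional subjects for further evaluation of safety or PK parameters as required". Section 3.2.1.4 says "SRMs will occur as needed to make determinations about enrollment and dose escalation according to the DLT-dependent mCRM".

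Stopping rule (c) in Section 3.2.1.5 applies if "the initial dose level is too toxic". No number is attached to it.

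**The concern.** The primary objective is to find the recommended dose for expansion with this model, and Section 1.1.3 reports no clinical data for DS-1205c. Two situations can arise at the first dose decision, and the text settles neither.

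- **No DLT in the first three subjects.** Nothing prevents the formal output from being the top listed dose, so the total daily dose could go from 400 to 1,600 mg. Footnote a rules out reading Table 3.1 as an implied ladder, and the three-subject condition governs when to escalate, not how far.
- **One DLT in the first three.** No dose is admissible. The plan has no step for that case, and rule (c) cannot be applied from the text because it has neither a criterion nor a tie to the 0.25 limit.

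At stake are subject safety in the first case and a consistent, reproducible decision in the second.

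**Working it through.** **Inputs.** Model (11.11.1): logit π(d) = log α + β log(d/800). Prior for (log α, log β) (11.11.2): means −1.1493 and −0.5514, SDs 2.0739 and 1.5228, correlation −0.1943. Target interval 0.16–0.33 and overdose limit Pr(π > 0.33) < 0.25 (11.11.3). Doses from Table 3.1.

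**Method.** Posterior ∝ prior × ∏ π(d)^x (1 − π(d))^(n−x), integrated numerically over (log α, log β). Different integrations agree to within about 0.004.

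**Step 1: reproduce the plan's figure.** The prior medians come out at 8.0% at 200 mg and 24.1% at 800 mg, against the stated approximate 8% and 24.5%. The printed prior has been read correctly, with d as the dose per administration. Before any data, the overdose probability at 200 mg is 0.256.

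**Step 2: posterior by dose.**

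| Data at 200 mg BID | Quantity | 200 | 400 | 600 | 800 | Output |
|---|---|---|---|---|---|---|
| 0/3 | overdose | 0.037 | 0.073 | 0.126 | 0.206 | all admissible |
| 0/3 | target | 0.094 | 0.138 | 0.174 | 0.204 | 800 mg |
| 1/3 | overdose | 0.368 | 0.486 | 0.555 | 0.598 | none |
| 1/6 | overdose | 0.120 | 0.231 | 0.320 | 0.380 | 400 mg |
| 2/6 | overdose | 0.402 | higher | higher | higher | none |

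For 1/6, the target probability is 0.308 at 200 mg and 0.353 at 400 mg, so 400 mg is recommended. For 2/6, β > 0 makes the overdose probability rise with dose, so failure at 200 mg settles the rest. Between three and six subjects, 1/4 at 200 mg is marginally outside the limit (0.254) and 1/5 is inside it (0.175).

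**Step 3: sensitivity.** Both first-cohort results are unchanged with correlation 0, with the printed SDs read as variances, and with total daily dose and reference 1,600 mg. Total daily dose with reference 800 mg would give 400 mg BID after 0/3, but 11.11.2 names 200 mg as the starting dose, which rules that reading out.

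**Step 4: how often each output arises.** For a true DLT rate p at 200 mg and three subjects, Pr(800 mg recommended) = (1 − p)³ and Pr(no admissible dose) = 1 − (1 − p)³.

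| p | 5% | 8% | 16% | 33% |
|---|---|---|---|---|
| 800 mg recommended | 86% | 78% | 59% | 30% |
| No admissible dose | 14% | 22% | 41% | 70% |

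**Step 5: an empty set is not the same as a toxic starting dose.** With 0/3 at 200 mg and 2/3 at 400 mg, 200 mg itself fails the limit (0.275), although nobody there had a DLT. Three more DLT-free subjects at 200 mg readmit it (0.098). One DLT among those three leaves it out (0.323).

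**Step 6: what a cap does.** After 0/3 at 200 mg a one-level cap gives 400 mg (overdose 0.073). After a further 0/3 at 400 mg the model again points to 800 mg, and the cap gives 600 mg (0.049). By then the overdose probability at 800 mg has fallen from 0.206 to about 0.13.

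**The case against.** The strongest reply is that these are model outputs, not decisions. The sponsor weighs the recommendation against clinical, PK and other data, may use lower or intermediate doses, and may expand any cohort (3.2.1.2). Safety Review Meetings with the investigators and the medical monitor decide on escalation (3.2.1.4). The second subject in a cohort starts at least 24 hours after the first, and subjects are hospitalised (6.1). All of this stands. A reader might infer from the 0/3 result that the fourth subject will receive 800 mg BID. The documents do not support that: the step is permitted, not required. What remains is that the discretion has no upper bound on the step. The sponsor's choice is referred back to 11.11.3, and the meetings act in line with the mCRM. The stagger and hospitalisation help detect harm but do not limit dose.

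For the 1/3 case, a reader might infer that the study stops, so that an acceptable starting dose would be abandoned about one time in five. The documents do not support that either. Nowhere is an empty admissible set equated with stopping, and expansion at 200 mg is open. The plan also starts at 200 mg although the prior alone puts it at 0.256, just outside the limit. For the same reason, a simulated comparison of how often the printed plan finds no dose would rest on a stopping rule that the plan does not contain. None is offered here. After 1/3 the plan is incomplete rather than unsafe.

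**Conclusion.** The point holds as two gaps in pre-specification. First, no section limits the escalation step, and with the printed prior the first DLT-free cohort of three produces a formal recommendation of 800 mg BID, the projected MTD, past two untested levels. Second, a first cohort with 1/3 leaves no listed dose within the overdose limit. The plan gives no consequence, and rule (c) has no criterion linked to the limit.

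The posterior figures rest only on the printed model and prior. The Step 4 percentages also assume a first cohort of exactly three with independent outcomes. Existing discretion reduces the risk but does not replace a stated bound in a study with no prior clinical data. This should be fixed, and it is cheap to fix. The model and prior need no change: after 0/3 at 200 mg and 1/3 at 400 mg, for example, the printed prior sensibly stays at 400 mg (600 mg has overdose probability 0.292).

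**What to change.** **Main change, in 11.11.3:**

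> The next cohort may not exceed the next untested listed level in Table 3.1 (or an intermediate dose below it).

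Footnote a of Table 3.1 should refer to this sentence.

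**Companion change, in 11.11.3 and 3.2.1.5, with the Synopsis aligned:**

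> If no listed dose meets the overdose limit, escalation is paused. As an exception to the limit, the 200 mg BID cohort may be expanded to at most 6 evaluable subjects if fewer than 2 DLTs and no Grade 5 DLT have occurred at that dose and a Safety Review Meeting agrees; the meeting may instead stop the study. Rule (c) is met if no listed dose meets the limit after 6 evaluable subjects at 200 mg BID, or earlier if no listed dose meets it and 2 or more DLTs have occurred at that dose.

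Six subjects fit the printed prior: 1/6 resumes at 400 mg (0.231) and 2/6 stops (0.402). The exception must be explicit, because expanding after 1/3 means dosing at a level the limit excludes (0.368). Expansion stays optional, and the Grade 5 condition prevents it after a single fatal DLT.

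If expansion is always agreed and no DLT is fatal, the chance of meeting rule (c) from the first level alone is Pr(≥2 of 3) + Pr(1 of 3) × Pr(≥1 of 3 more). At p = 8% this is 0.018 + 0.203 × 0.221 = 0.063. At 5%, 16% and 33% it is 0.027, 0.207 and 0.566.

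**Cost.** About six subjects (three each at 400 and 600 mg) before 800 mg, within the planned 18, and up to three more at 200 mg before a stop for toxicity.
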